1. BACKGROUND

1.1 Acute Myeloid Leukemia

Adult acute myeloid leukemia (AML) is the most common type of leukemia in adults, accounting for approximately 25% of leukemia diagnoses, with an estimated 19,950 new cases and an estimated 10,430 patients will die from AML this year in the US ([NCI 2016](#); [Deschler et al. 2006](#)). The 5-year survival rate in patients with AML is approximately 25%. AML evolves rapidly and develops resistance to therapy because of its polyclonal and heterogeneous features ([Ferrara et al. 2013](#)). Cytogenetic and molecular mutation testing may be important for risk assessment and prognosis, but they are not predictive. So far, ascertaining a specific mutation does not predict what therapy is likely to work ([Patel et al. 2012](#)).

AML patients initially respond well to the decades' old and still standard 3 + 7 induction regimen if they are candidates for this intensive therapy. Response and survival are associated with multiple factors, including patient age, performance status, antecedent hematologic conditions (de novo vs. secondary AML), and cytogenetic and molecular features. Responses in the second line of therapy rely on these prognostic factors but also include the achievement of minimal residual disease status and the duration and type of response, e.g., complete response (CR) or CRi (complete response with incomplete bone marrow recovery) in the first line ([Chen et al. 2015](#)). Patients in first relapse with a first CR duration of 12 months or longer are offered high-dose cytarabine-based regimens. These include fludarabine with cytarabine and idarubicin, clofarabine with idarubicin and cytarabine, cladribine with idarubicin and cytarabine, twice daily fludarabine, cytarabine, or high-dose cytarabine-based investigational approaches. For patients in first salvage with a first CR duration <12 months and all patients in second salvage or beyond, Phase 1 to 2 investigational approaches are reasonable ([Kantarjian 2016](#)).

1.2 Liposomal Annamycin

Doxorubicin is one of the most effective antitumor agents against hematological malignancies, including AML, and certain human solid tumors such as breast carcinoma and osteosarcoma. Its use is limited by myelosuppression, chronic cardiotoxicity, and natural or acquired drug resistance. Important advances in understanding the mechanisms of acquired resistance to doxorubicin and other structurally unrelated antitumor agents have occurred recently. Overexpression of a membrane glycoprotein, P-glycoprotein, which acts as a drug efflux pump, mediates acquired resistance to doxorubicin in some *in vitro* systems and *in vivo* animal tumor models ([DeVita et al. 1993](#)). Overexpression of P-glycoprotein occurs in a significant number of patients when their tumors progress or relapse after treatment with doxorubicin. No standard regimen exists for the treatment of patients with relapsed AML, particularly in patients with first remission duration of less than 1 year.

Extensive efforts have been devoted to the synthesis of anthracycline analogs with improved properties. Initial efforts were directed towards analogs with reduced cardiotoxicity ([Dalton et al. 1993](#); [Moscow et al. 1988](#); [Consoli et al. 1996](#)). More recently, triggered by the discovery of multidrug resistance and identification of P-glycoprotein, the efforts have focused on analogs with non-cross-resistant properties ([Acton et al. 1984](#); [Ganapathi et al. 1989](#); [Barbieri et al. 1987](#); [Priebe et al. 1993](#)). Several non-cross-resistant analogs have been identified. They all have in common a markedly increased lipophilicity. Some of them have a similar mechanism of cytotoxicity to that of doxorubicin, i.e., topoisomerase II inhibition. Others have a different mechanism of action, i.e., DNA alkylation ([Acton et al. 1984](#)).

Liposomes have been used extensively as carriers of doxorubicin and daunorubicin ([Gabizon et al. 1982](#); [Rahman et al. 1986](#)). Liposomal doxorubicin was found to be less cardiotoxic and more active than doxorubicin in models of liver metastases in mice ([Mayhew et al. 1983](#); [Herman et al. 1983](#)). Clinical studies have been conducted with different liposomal formulations of doxorubicin. These trials have shown a maximum-tolerated dose (MTD) similar to that of free doxorubicin, a significant reduction of certain toxicities, such as gastrointestinal and vesicant effects, and an unchanged dose-limiting toxicity, i.e., myelosuppression. These studies have also suggested a reduced cardiotoxic potential.

Annamycin is an anthracycline antibiotic with a mechanism of action that appears to be inhibition of topoisomerase-II. This drug was selected for its lack of cross-resistance and a high affinity for lipid membranes ([Perez-Soler et al. 1990](#)). Because of this latter property, annamycin is an ideal compound for liposome entrapment, thus as this drug is completely insoluble in water solutions, liposomes can be used as a carrier for its intravenous administration. Liposomal annamycin was developed to combine the intrinsic favorable properties of the compound (lack of cross-resistance) with the potential advantages associated with liposome delivery (reduced cardiotoxicity and preferential distribution to certain organs), as well as the potential for resisting multidrug-resistant (MDR) activity ([Perez-Soler et al. 1997](#); [Kolonias et al. 1999](#)). A liposomal formulation of annamycin was developed at MD Anderson Cancer Center that has high entrapment efficiency, physical stability, and chemical stability.

1.3 Nonclinical Studies

The *in vitro* cytotoxicity of liposomal annamycin was tested on a panel of 4 different parental cell lines and their respective MDR-1-expressing cell lines ([Zou et al. 1994](#)). In all MDR cell lines tested (KB-V1, P388/Dox, CEM/Vbl, and 8226/R), there was minimal resistance to annamycin; however, as expected, resistance to doxorubicin was high. Studies with MDR modulators and metabolic inhibitors indicated significant differences in the cellular transmembrane transport systems between doxorubicin and annamycin and suggest that annamycin efflux is not mediated by P-glycoprotein MDR ([Perez-Soler et al. 1994](#)).

In vivo, liposomal annamycin has shown lack of cross-resistance in KB-VI human xenografts (an MDR-resistant cell line) and enhanced antitumor activity compared with doxorubicin in several mouse tumor models such as leukemia (L-1210), melanoma (B16), reticulosarcoma (M5076), and Lewis lung carcinoma cells ([Zou et al. 1994](#); [Perez-Soler et al. 1990](#)). Results in KB and KB-VI human xenografts demonstrate that liposomal annamycin was at least as effective as doxorubicin ([Zou et al. 1994](#)). Liposomal annamycin was more active than doxorubicin in a leukemia L-1210 mouse tumor model ([Perez-Soler et al. 1990](#)).

In mice, at a single intravenous dose of 15.7-mg/kg liposomal annamycin, myelosuppression was noted. With weekly intravenous doses of 5.2-mg/kg liposomal annamycin for 6 weeks or 3.1- and 4.2-mg/kg liposomal annamycin for 10 weeks, the cardiotoxicity of liposomal annamycin was less than equitoxic doses of doxorubicin ([Zou et al. 1995](#)). In dogs, a single 15-minute intravenous infusion of up to 1.42-mg/kg liposomal annamycin was well tolerated, with no clinically significant adverse effects, hematological and chemical changes, and pathological changes ([Zou et al. 1995](#)).

Additional information about the nonclinical data with liposomal annamycin can be found in the Investigator's Brochure.

1.5 Rationale for the Current Study

Based on the positive clinical results in subjects with acute leukemia in 2 previous clinical studies of single-agent liposomal annamycin (Study No. AR522-21 and Study No. CP-103; see [Section 1.4](#)), the nonclinical data showing both lack of cross-resistance with anthracyclines (which is the standard of care for first-line treatment of AML), the increased activity in certain leukemia cells lines compared with doxorubicin, and the potential for decreased cardiotoxicity, the current study (Study No. MB-104) was designed to explore liposomal annamycin in a Phase 1/2 investigation for the treatment of relapsed/refractory AML. Safety, pharmacokinetics, and clinical response will be evaluated. The objective of the study is to determine the safety and tolerability of annamycin, identify dose-limiting toxicities, and define the MTD, as well as the recommended Phase 2 dose (RP2D). The design of this study incorporates a 3+3 dose-escalation design and expansion at the RP2D for evaluation of clinical efficacy in up to 21 additional subjects.

1.6 Consideration of Cardiotoxicity in the Current Study

On the basis of concerns about the possible risk of cardiotoxicity in subjects who have likely received prior anthracycline therapy ([Zamorano et al. 2016](#); [Gianni et al. 2008](#)), [Table 1](#) and [Table 2](#) establish some important considerations, including baseline risk factors and maximal

prior anthracycline doses, to be calculated on the basis of equivalent anthracycline exposure anticipated. This protocol incorporates clear criteria for risk factors, as well as prior anthracycline exposure, to exclude subjects at cardiac risk from this study.

Table 1: Baseline Risk Factors for Cardiac Disease ([Zamorano et al. 2016](#))

Current Myocardial Disease:
Heart failure (with either preserved or reduced ejection fraction)
Asymptomatic LV dysfunction (LVEF <50% or high natriuretic peptide)
Evidence of CAD (previous MI, angina, PCI or CABG, myocardial ischemia)
Moderate and severe VHD with LVH or LV impairment
Hypertensive heart disease with LVH
Cardiomyopathy (hypertrophic, dilated, or restrictive)
Cardiac sarcoidosis with myocardial involvement
Significant cardiac arrhythmias
Demographic and Other CV Risk Factors:
Age (>65 years)
Family history of premature CV disease
Arterial hypertension
Diabetes mellitus
Hypercholesterolemia
Lifestyle Risk Factors:
Smoking
High alcohol intake
Obesity
Sedentary

Abbreviations: CABG = coronary artery bypass graft; CAD = coronary artery disease; CV = cardiovascular; LV = left ventricular; LVEF = left ventricular ejection fraction; LVH = left ventricular hypertrophy; MI = myocardial infarction; PCI = percutaneous coronary intervention; VHD = valvular heart disease.

Table 2: Cardioprotective Measures for Anthracycline Drugs (adapted from [Zamorano et al. 2016](#))

Potential Cardioprotective Measures for Anthracycline Drugs and Analogues by Limitation of Cumulative Doses	
Drug	Conversion Factor (Daunorubicin Equivalents)
Daunorubicin	1
Doxorubicin	2.2
Epirubicin	1.1
Mitoxantrone	5
Idarubicin	5.3

A value of 551 mg/m^2 will be used as the correlative value for liposome-encapsulated annamycin for purposes of assessment of maximal exposure, with a conversion factor of 1.

Consideration of the equivalence with conversion factor and sample calculations of these anthracyclines to calculate prior exposure are provided in [Appendix E](#).

2. STUDY OBJECTIVES

The primary objective of this study is to evaluate the safety and identify the RP2D of liposomal annamycin for the treatment of subjects with AML that is refractory to or relapsed after standard induction therapy.

Secondary objectives:

1. Pharmacokinetics of annamycin and its metabolite, annamycinol
2. Preliminary assessment of the antileukemic activity of liposomal annamycin as second-line therapy for subjects with refractory or relapsed AML based on established response criteria, including complete response (CR), partial response (PR), event-free survival (EFS), overall survival (OS; Kaplan-Meier), and time to and duration of remission/response

3. STUDY DESIGN

3.1 Design Summary

This is a multicenter, open-label, dose-escalation study that will determine the MTD and RP2D of liposomal annamycin as a single agent for the treatment of subjects with AML that is refractory to or relapsed after standard induction therapy.

During the dose-escalation phase of the study, eligible subjects could have received any number of previous therapies for their relapsed AML as long as the prior anthracycline cumulative dose is below the recommended noncardiotoxic level (as defined in [Table 2](#) and [Appendix E](#)). During the expansion phase of the study, after the MTD or RP2D has been established, study treatment will be second-line therapy, thus subjects could not have received prior therapy for their relapsed AML.

Enrollment will occur in cohorts of 3 subjects in a conventional 3+3 escalating dose design, starting at a dose level of 100 mg/m²/day administered for 3 days. Dose escalation will take place on the basis of safety assessments in this first cohort with the next dose of liposomal annamycin escalated to 120 mg/m² in the absence of safety concerns.

For each dose level, groups of 3 subjects will receive a treatment cycle of liposomal annamycin daily as a 2-hour IV infusion for 3 consecutive days followed by 18 days off study drug (i.e., the induction treatment cycle = 21 days). If no subject experiences a dose-limiting toxicity (DLT), based on National Cancer Institute (NCI) Common Terminology Criteria for Adverse Events (CTCAE) v5, which constitutes a definite study drug-related irreversible or not medically manageable Grade 3 or higher toxicity, further defined in [Section 3.4](#), during the induction treatment cycle through Day 28, the subsequent group of 3 subjects will receive the next higher liposomal annamycin dose. However, if 1 of the 3 initial subjects experiences a DLT, the cohort of subjects at that dose level will be expanded to 6 subjects. If at least 2 of the 6 subjects

experience a DLT, this will be considered a nontolerated dose and then 3 subjects will be treated at a lower dose.

The MTD is defined as the highest dose of liposomal annamycin at which fewer than 2 (of a cohort of up to 6) subjects experience a DLT.

The RP2D is defined as the optimal dose to be determined by the Sponsor in conjunction with the Safety Review Committee/Consultant (SRC), consisting of at least 1 to up to 3 independent consultants, on the basis of review of available clinical and laboratory safety and efficacy data. Up to 21 additional subjects will be enrolled at either the MTD or RP2D to better define toxicity and evaluate efficacy at this dose. Therefore, up to 33 subjects will be enrolled in this study: up to 12 subjects in the dose-escalation phase and up to 21 additional subjects at the MTD or RP2D.

The Medical Monitor and the SRC will continually review all data and decide if the study should continue and if any changes to the protocol before restarting enrollment must be made.

If a subject discontinues treatment for reasons other than study drug-related adverse events such that safety or efficacy of the drug cannot be fully evaluated during the induction cycle, a replacement subject may be enrolled; these circumstances will be reviewed on a case-by-case basis by the SRC in conjunction with the Sponsor.

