Methodology:	
This is a multicenter, open-label, dose-escalation study that will determine the maximum-tolerated dose (MTD) and RP2D of liposomal annamycin as a single agent for the treatment of subjects with AML that is refractory to or relapsed after standard induction therapy.
 
During the dose-escalation phase of the study, eligible subjects could have received any number of previous therapies for their relapsed AML as long as the prior anthracycline cumulative dose is below the recommended noncardiotoxic level). During the expansion phase of the study, after the MTD or RP2D has been established, study treatment will be second-line therapy, thus subjects could not receive prior therapy for their relapsed AML.
 
Enrollment will occur in cohorts of 3 subjects in a conventional 3+3 escalating dose design, starting at a dose level of 100 mg/m²/day administered for 3 days. Dose escalation will take place on the basis of safety assessments in this first cohort with the next dose of liposomal annamycin escalated to 120 mg/m² in the absence of safety concerns.
 
For each dose level, groups of 3 subjects will receive a treatment cycle of liposomal annamycin daily as a 2-hour intravenous infusion for 3 consecutive days followed by 18 days off study drug (i.e., the induction treatment cycle = 21 days).. If no subject experiences a dose-limiting toxicity (DLT), based on National Cancer Institute (NCI) Common Terminology Criteria for Adverse Events (CTCAE) v5, which constitutes a study drug-related irreversible or not medically manageable Grade 3 or higher toxicity during the induction treatment through Day 28, the subsequent group of 3 subjects will receive the next higher liposomal annamycin dose. However, if 1 of the 3 initial subjects experiences a DLT, the cohort of subjects at that dose level will be expanded to 6 subjects. If at least 2 of the 6 subjects experience a DLT, this will be considered a nontolerated dose and then 3 subjects will be treated at a lower dose.

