	
The MTD is defined as the highest dose of liposomal annamycin at which fewer than 2 (of a cohort of up to 6) subjects experience a DLT.
 
The RP2D is defined as the optimal dose to be determined by the Sponsor in conjunction with an independent Safety Review Committee/Consultant (SRC), consisting of at least 1 independent consultant, on the basis of review of available clinical and laboratory safety and efficacy data. Up to 21 additional subjects will be enrolled at either the MTD or RP2D, to better define toxicity and evaluate efficacy at this dose.
 
If a subject discontinues treatment for reasons other than study drug-related adverse events such that safety and efficacy of the drug cannot be fully evaluated during the induction cycle, a replacement subject may be enrolled; these circumstances will be reviewed on a case-by-case basis by the SRC in conjunction with the Sponsor.

Number of Subjects:	
Three subjects minimum (6 maximum) for each dosing cohort. Evaluation of a RP2D based on the aggregate assessment of data will be determined by the SRC in conjunction with the Sponsor, with consideration of additional dose exploration based on safety assessments. Up to 21 additional subjects will be enrolled at the MTD or RP2D to better define toxicity and evaluate efficacy at this dose. Therefore up to 33 subjects will be enrolled in this study: up to 12 subjects in the dose-escalation phase and up to 21 additional subjects at the MTD or RP2D.

Study Drug:	
Annamycin is a lipophilic anthracycline antibiotic that incorporates 4 structural modifications from doxorubicin: 2'-iodo, 3'-hydroxy, 4'-epi, and 4-demethoxy doxorubicin.
 
Liposomal annamycin is supplied in 50-mL vials containing annamycin as a lyophilized powder.
 
Subjects will be treated daily for 3 consecutive days with a 2-hour intravenous infusion of liposomal annamycin followed by 18 days off liposomal annamycin (i.e., 1 treatment cycle = 21 days). The starting dose of liposomal annamycin (dose for subjects in Cohort 1) is 100 mg/m²/day. The liposomal annamycin doses will be escalated up to 120 mg/m²/day in the next cohort in the absence of safety concerns.

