3.2 Dosing

The initial group of 3 subjects will be treated with a 2-hour intravenous infusion of 100-mg/m²/day (Dose Level 1) liposomal annamycin daily for 3 consecutive days followed by 18 days off study drug (i.e., 1 treatment cycle = 21 days). Provided that no subject experiences a DLT (defined in [Section 3.4](#)) during the induction treatment cycle through Day 28, the ensuing group of 3 subjects will receive 120-mg/m²/day (Dose Level 2) liposomal annamycin.

The liposomal annamycin dose levels planned for investigation are outlined in [Table 3](#). The starting dose is Dose Level 1.

Table 3: Liposomal Annamycin Dose Levels

[figure not shown]
Dose Level Designation	Liposomal Annamycin Dose (mg/m ² /day) × 3 days
-1	90
1	100
2	120

For each dosing cohort, if 1 of the 3 initial subjects experiences a DLT ([Section 3.4](#)), the cohort of subjects at that dose level will be expanded to 6 subjects ([Figure 1](#)). If at least 2 of the 6 subjects experience a DLT, then 3 subjects will be treated at a lower dose. If a DLT occurs in at least 2 out of 6 subjects at Dose Level 1, the next 3 subjects will be enrolled into Dose Level -1. The MTD is defined as the highest dose of liposomal annamycin at which fewer than 2 (of a cohort of up to 6) subjects experience a DLT. The RP2D is defined as the dose to be

explored in the expansion phase portion of the study, based on the aggregate data of safety and efficacy.

Figure 1: Schematic of Dosing Plan

Liposomal annamycin will be administered for a single induction cycle.

Abbreviations: DLT = dose-limiting toxicity; HSCT = hematopoietic stem cell transplantation.

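### The stated maximum of 12 escalation subjects equals two dose levels of 6, but three levels are planned and the written rules can require 15 or 18

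*Combined protocol and SAP*

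**What the plan says.** Section 3.1 gives the enrolment limits: "up to 33 subjects will be enrolled in this study: up to 12 subjects in the dose-escalation phase and up to 21 additional subjects". The Synopsis (Number of Subjects) repeats "up to 12 subjects in the dose-escalation phase and up to 21 additional subjects at the MTD or RP2D" and sets the cohort size: "Three subjects minimum (6 maximum) for each dosing cohort". The total of 33 appears again in the Synopsis (Statistical Analyses) and in Section 10.

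Table 3 in Section 3.2 lists three levels: -1, 1 (the start) and 2. Section 3.2 applies the expansion from 3 to 6 subjects after one DLT to every dosing cohort, so Level -1 is included.

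On de-escalation, Section 3.2 says: "If at least 2 of the 6 subjects experience a DLT, then 3 subjects will be treated at a lower dose". Section 3.1 ("this will be considered a nontolerated dose and then 3 subjects will be treated at a lower dose") and the Synopsis (Methodology) agree. The receiving level is named only for a failed Level 1: "If a DLT occurs in at least 2 out of 6 subjects at Dose Level 1, the next 3 subjects will be enrolled into" Level -1.

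The only written trigger for opening Level 2 is no DLT at Level 1. The text calls the design a conventional 3+3 but does not say what follows 1/6 at Level 1. The MTD is the highest dose at which "fewer than 2 (of a cohort of up to 6) subjects experience a DLT".

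**The concern.** A limit of two levels times 6 cannot cover every path through three levels that may each hold 6. If Level 2 fails, the lower-dose sentence requires more subjects below it, and the running count can already be 9 to 12 by then.

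If 12 is enforced, a cohort or an expansion that the rules call for cannot be enrolled. If subjects return to Level 1, Levels 1 and 2 can both end with at least 2/6 DLTs and nobody treated at Level -1, so no tested level meets the MTD definition. If 12 is not enforced, the maximum in the approved protocol is too low.

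**Working it through.** **The plan's own figure.** The document does not show how 12 was reached. Two levels × 6 = 12, and 12 + 21 = 33, so both figures reproduce exactly.

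**Longest paths**, with at most 6 subjects per dose level in total:

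- *R1, lower dose means back to Level 1.* Level 1 0/3 (3 subjects); Level 2 1/3, then at least 2/6 (9); 3 more at Level 1 (12), giving at least 2/6 there; 3 at Level -1 (15); 1/3 there, so expand to 6 (18). That is 3 + 6 + 3 + 6 = 18.
- *R2, lower dose means Level -1, and Level 2 opens only after 0/3.* Level 1 0/3 (3); Level 2 at least 2/6 (9); 3 at Level -1 (12); 1/3 there, expand (15). That is 3 + 6 + 6 = 15.
- *R3, as R2, but 1/6 at Level 1 also escalates.* 6 + 6 + 6 = 18.

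Under R1, letting 1/6 escalate changes nothing: Level 1 already holds 6, so nobody is added there.

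**How often.** The documents give no DLT risks, so I searched all risks that do not fall with dose, in 1-point steps from 1% to 99%. I took 2 or 3 DLTs in the first three as closing a level, which is conventional but not written. With p the DLT risk at the level concerned:

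- q0 = P(0/3 at Level 1) = (1−p)³
- s = P(1/3, then 0/3 at Level 1) = 3p(1−p)² × (1−p)³
- r = P(at least 2 in the second three at Level 1) = 3p²(1−p) + p³
- f6 = P(Level 2 fails at 6) = 3p(1−p)² × [1 − (1−p)³]
- f3 = P(Level 2 fails at 3) = 3p²(1−p) + p³
- m1 = P(1/3 at Level -1) = 3p(1−p)²

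P(more than 12) at its largest, with risks at Levels -1/1/2:

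- R1: q0·f6·r + q0·f3·r·m1. At 33/36/57%: 0.2621 × 0.2910 × 0.2955 + 0.2621 × 0.6043 × 0.2955 × 0.4444 = 0.0225 + 0.0208 = 0.0433.
- R2: q0·f6·m1. At 17/17/43%: 0.5718 × 0.3415 × 0.3513 = 0.0686.
- R3: q0·f6·m1 + s·(f6 + f3·m1). At 18/18/48%: 0.5514 × 0.3346 × 0.3631 + 0.2002 × (0.3346 + 0.4700 × 0.3631) = 0.0670 + 0.1011 = 0.168.

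| | R1 | R2 | R3 |
|---|---|---|---|
| Escalation maximum | 18 | 15 | 18 |
| Plus 21 in expansion | 39 | 36 | 39 |
| Largest P(more than 12) | 4.3% | 6.9% | 16.8% |
| P(more than 12) at assumed risks 10/15/30% | 1.3% | 4.3% | 11.2% |

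**If 12 is enforced under R1.** The first term, q0·f6·r, is the chance that Levels 1 and 2 both fail with 12 subjects used and Level -1 untested. It is 0.6141 × 0.2897 × 0.0607 = 0.011 at 10/15/30%, and at most 0.2621 × 0.3415 × 0.2955 = 0.026 (36% and 43% at Levels 1 and 2). In the second term the expansion of Level -1 does not fit. Under R2 and R3, Level 1 at 0/3 or 1/6 still meets the MTD definition; what is lost is the cohort or expansion at Level -1.

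**The case against.** The strongest reply is that 12 is what the design intends. If Level 2 fails and Level 1, at 0/3 or 1/6, simply stands as the MTD, no path passes 6 + 6 = 12. That is coherent with the MTD definition, but it leaves the instruction "then 3 subjects will be treated at a lower dose" not carried out. The conflict then lies in that sentence rather than in the count.

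Other limits also stand. The Figure 1 schematic was not available here and may name the level or the action after 1/6; if so, the text still has to agree with it. The Synopsis allows for further dose exploration, and the sponsor and safety review committee have discretion over the RP2D, but neither removes a fixed limit of 12 stated in the same paragraph. The expansion is an upper limit, so 33 can absorb the excess; the 12 cannot.

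Eighteen also rests on pooling subjects added at Level 1 with the first three. If they form a new cohort that may itself expand, the count can reach 3 + 6 + 6 + 6 = 21.

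A reader might infer that any use of Level -1 breaks the limit, or that the trial is likely to overrun 33. The documents support neither. Level 1 failing straight to Level -1 needs at most 6 + 6 = 12, and one R1 path through all three levels also uses 12 (6 at Level 1, 3 at Level 2, 3 at Level -1). The total passes 33 only if most or all of the 21 expansion places are filled as well.

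**Conclusion.** Wrong as written, and minor. Carrying out the written rules can take escalation to 18 (R1 and R3) or 15 (R2), against a stated 12: an understatement of 6 or 3. The total would be 39 or 36 against 33, before replacements, and only with a full expansion.

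The counts assume at most 6 subjects per dose level and that the lower-dose sentence is followed. Fifteen holds only if 1/6 at Level 1 does not escalate, so it is not a safe replacement for 12. The probabilities are upper limits over assumed risks, not forecasts.

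A reader might also infer that the main analysis is undermined. It is not: Section 10 plans descriptive statistics only, and no estimate, test or error rate depends on 12.

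**What to change.** Reconcile the Synopsis (Methodology and Number of Subjects), Sections 3.1 and 3.2, and Figure 1 on three points: which level is meant by a lower dose after a failed Level 2; what follows 1/6 at Level 1; and whether subjects added at a level count with those already treated there. This review takes no position on which dosing rule is right.

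Then restate the escalation maximum to match; 18 covers R1 to R3. For the total, either restate it (up to 18 + 21 = 39) in the Synopsis (Number of Subjects and Statistical Analyses) and Sections 3.1 and 10, or keep 33 and state that the expansion shrinks by the excess, to as few as 33 − 18 = 15. State also that the limit does not stop a required cohort. If Level 1 at 0/3 or 1/6 is meant to stand with no further subjects, keep 12 and reword the lower-dose sentence.

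The cost is a protocol amendment with the approvals in Sections 13.2 and 16. Compared with enforcing 12, expected extra escalation enrolment is at most 0.16 subjects under R1 and 0.21 under R2. Under R3 it cannot exceed 6 × 0.168, about 1 subject.

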4.3 Subject Withdrawal

Subjects may voluntarily withdraw from the study at any time for any reason and without prejudice to further treatment or the Investigator may withdraw subjects if necessary.

Subjects who are removed from the study will undergo all study evaluations described for the End of Study visit ([Section 6.4](#)). The reasons for withdrawal will be recorded.

The reasons for which a subject may be prematurely discontinued include the following:

1. Subject has unacceptable toxicity, subject demonstrates manifestations of cardiotoxicity, or subject has >10% decrease in ejection fraction based on scans. All subjects who are discontinued as a result of an adverse event should be followed for as long as necessary to document the resolution or stabilization of the event.
2. Subjects with disease progression
3. Subject withdrawal of consent
4. Investigator's discretion
5. General or specific changes in the subject's condition that renders the subject ineligible for further treatment
6. If pregnancy occurs or is suspected during study drug treatment, amnomycin must be discontinued immediately. The subject should be referred to an obstetrician/gynecologist experienced in reproductive toxicity for further evaluation and counseling. If none is immediately available, contact Moleculin Biotech for a referral.
7. If the subject's continued participation poses unacceptable risk for any other reason or if they are not compliant with the study

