4.3.2 Subject Replacement

Subjects withdrawing in the cohort dose-escalation period for reasons other than toxicity who have not taken all 3 doses during the induction cycle and/or fail to complete restaging after completion of the treatment cycle such that safety is not evaluable will be replaced. However, subjects experiencing a DLT in the dose-finding cycle will not be replaced.

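### The Synopsis, Section 3.1 and Section 4.3.2 give different subject-replacement rules, and with no defined efficacy population an early failure can be replaced and left out of the response rate

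*Combined protocol and SAP*

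**What the plan says.** Three places in the current text govern replacement.

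- **Section 3.1.** The trigger is "If a subject discontinues treatment for reasons other than study drug-related adverse events", and the condition is "such that safety or efficacy of the drug cannot be fully evaluated during the induction cycle, a replacement subject may be enrolled". No study phase is named. On who decides: "these circumstances will be reviewed on a case-by-case basis by the SRC in conjunction with the Sponsor".
- **Synopsis, Methodology.** The trigger and the review arrangement are the same, but the condition reads "such that safety and efficacy of the drug cannot be fully evaluated during the induction cycle, a replacement subject may be enrolled".
- **Section 4.3.2.** The rule covers "Subjects withdrawing in the cohort dose-escalation period for reasons other than toxicity" who miss a dose and/or "fail to complete restaging after completion of the treatment cycle such that safety is not evaluable will be replaced". It adds that "subjects experiencing a DLT in the dose-finding cycle will not be replaced".

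Section 4.3 lists "Subjects with disease progression" among the reasons for discontinuation. Section 7.1.1 names leukemia response rate as the primary efficacy variable and assesses it in subjects evaluable for efficacy, without defining that set. Section 7.2 places the response marrow 15 to 35 days after the start of therapy. Section 10 fixes the safety population (everyone who received at least one dose) but names no efficacy population.

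**The concern.** The versions differ in ground (safety and efficacy, safety or efficacy, safety alone), in phase (unrestricted, or escalation only) and in force (*may* or *will*). A site or the Safety Review Committee (SRC) could reach different decisions on the same subject depending on the section consulted.

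The efficacy ground matters most. A subject who stops early for progression has not stopped for a drug-related adverse event and may have no marrow in the response window. Section 3.1 allows that subject to be replaced. Because the efficacy-evaluable set is undefined, nothing keeps the subject in the response denominator. Subjects lost this way are likely to be non-responders, so the reported rate would move upward. The expansion of up to 21 subjects is meant partly to evaluate efficacy, and under Section 3.1 the choice of the recommended Phase 2 dose also draws on efficacy data.

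**Working it through.** **1. The plan's own figure.** Section 3.1 gives up to 12 subjects in escalation and up to 21 in expansion: 12 + 21 = 33, which agrees with the stated maximum. The documents do not say whether replacements count within the 12, 21 or 33. They state no response target, alpha or power.

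**2. The rules side by side.**

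| | Synopsis | Section 3.1 | Section 4.3.2 |
|---|---|---|---|
| Not evaluable for | safety and efficacy | safety or efficacy | safety |
| Phase | not restricted | not restricted | escalation |
| Force | may | may | will |
| Decision | SRC with Sponsor | SRC with Sponsor | none stated |

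**3. Three subjects under the three rules** (each stops treatment for a reason that is not drug-related).

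- Escalation, observed for DLT to Day 28 without one, no response assessment. Section 3.1: may be replaced. Section 4.3.2: no ground. Synopsis: no ground if *and* requires both.
- Escalation, response assessed, safety not evaluable. Section 4.3.2: must be replaced. Section 3.1: may be. Synopsis: no ground if *and* requires both.
- Expansion, stops during dosing for progression, no marrow. Section 3.1: may be replaced. Section 4.3.2 does not cover expansion. Synopsis: depends on whether safety is also not evaluable.

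**4. Effect on the response rate.** Let N be the number dosed, p the true response rate among them, and f the share who are unassessed non-responders and left out. Responders number Np and the denominator is N(1−f), so the reported rate is p/(1−f). The documents give neither p nor f, so both are assumed. For p = 20%:

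- f = 5%: 0.20/0.95 = 21.1%
- f = 10%: 0.20/0.90 = 22.2%
- f = 20%: 0.20/0.80 = 25.0%
- f = 30%: 0.20/0.70 = 28.6%

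For scale, the standard error at 20% with 21 subjects is √(0.20 × 0.80/21) = 8.7 points, so the shift of 1.1 to 8.6 points runs from about an eighth of a standard error to about one.

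Replacement is not needed for this bias. With 21 dosed, 4 unassessed and 4 responders, leaving out the 4 unassessed gives 4/17 = 23.5%, against 4/21 = 19.0%. If those 4 were replaced and everyone dosed stayed in the denominator, no such inflation would arise.

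**5. Effect on escalation.** Here p is an assumed DLT rate and q = 1−p. A dose passes the 3+3 rule with probability q³ + 3pq²·q³. At p = 0.3 this is 0.343 + 0.441 × 0.343 = 0.494. Suppose one observed DLT-free subject among the first three is replaced and only the new result counts. The probability becomes 0.343 × 0.7 + (0.343 × 0.3 + 0.441 × 0.7) × 0.343 = 0.240 + 0.141 = 0.381. At DLT rates of 0.2 and 0.4 the change is 0.709 to 0.619 and 0.309 to 0.204. The dose becomes harder to pass.

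**The case against.** Several arguments on the other side have force.

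- *The trigger is narrow.* Section 3.1 requires that treatment be discontinued, and treatment is three daily infusions in a single cycle. A subject who takes all three and then progresses has not clearly discontinued. This stands as one reading. However, the protocol also calls the 21 days the treatment cycle, and a subject who stops during the dosing days for a qualifying reason is covered on any reading.
- *The Synopsis may agree with Section 3.1.* Its *and* could mean that the two cannot both be evaluated, which amounts to *or*. That is possible, but Section 4.3.2 still conflicts with both.
- *The DLT-complete escalation subject without a response is rare.* This is probably true, since someone who leaves early will often miss the window to Day 28.
- *Response is a secondary, preliminary objective with descriptive analysis only.* This limits the consequence, but a descriptive rate still needs a stated denominator.

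A reader might infer that the Sponsor alone can swap subjects out. The text does not say so: an external SRC reviews each case with the Sponsor. That review has no stated criteria, and the committee may be a single consultant.

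A reader might also take f = 20% from the earlier leukemia study in Section 1.4, where 8 of 10 Phase 2 subjects completed dosing. That study was in acute lymphocytic leukemia, reasons for non-completion are not given, and its 62% is clearing of circulating blasts, not response. It does not supply f for this trial.

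**Conclusion.** The inconsistency is real and should be corrected. The documents show three differing replacement rules, an efficacy ground in Section 3.1 that can reach early progression, and no definition of the set on which response is calculated. Together these allow early failures to leave the response rate, which would push it upward.

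The size is conditional. A true 20% reading as 21.1% to 28.6% rests on an assumed f of 5% to 30%, and on those left out being non-responders. If they would have responded at rate r, the reported rate is (p − fr)/(1−f), which equals p when r = p. No document says that replaced subjects will be excluded; the point is that nothing says they will be kept.

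A reader might infer that replacement makes the maximum tolerated dose too lenient. The documents do not support that. Section 4.3.2 bars replacing subjects with a DLT in the dose-finding cycle, and replacing a DLT-free subject is conservative. What remains in escalation is uncertainty over whether such a subject may be replaced at all. Nor does the text require enrolment to continue until 21 subjects are evaluable, since 21 and 33 are ceilings.

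**What to change.** 1. Reconcile the Synopsis, Section 3.1 and Section 4.3.2 into one replacement rule based on DLT or safety evaluability, as Section 4.3.2 already has it. Delete efficacy non-evaluability as a ground in the Synopsis and Section 3.1, and have both refer to Section 4.3.2.
2. In Sections 7.1.1 and 10, define the response-rate denominator as all dosed subjects, including any who are replaced, with those lacking a response assessment counted as non-responders. Make the matching change in the Synopsis.
3. State that any added expansion subjects add to the denominator and do not substitute for anyone, and say whether replacements count within the 12, 21 and 33.

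Item 2 removes the bias; item 1 alone would not. Whether an expansion subject who is not evaluable for safety may be replaced is the Sponsor's choice, provided the rule is written once and the denominator keeps everyone.

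The cost is wording only, with no new procedures. The reported response rate may be slightly lower, and fewer than 21 expansion subjects may have a marrow result.
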